10. STATISTICAL CONSIDERATIONS

10.1. Hypotheses

This study is designed to estimate the relative bioavailability of each test treatment to the reference treatment (A vs. B; C vs. E and D vs. E) in both study parts in the fasted state.

No formal hypothesis will be tested. For each pharmacokinetic endpoint (except for time of occurrence of C_{max} [t_{max}] and t_{lag}), point estimates and corresponding 90% confidence intervals will be constructed for the ratio of the geometric mean of the test treatment to the geometric mean of the reference treatment, $\mu(\text{test})/\mu(\text{reference})$.

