10.3.1. Primary Analyses

10.3.1.1. Pharmacokinetic Analyses

Pharmacokinetic analyses will be the responsibility of the Clinical Pharmacology Modeling & Simulation department within GSK or their designee. Plasma DTG concentration-time data will be analyzed by non-compartmental methods with Phoenix WinNonlin. Calculations will be based on the actual sampling times recorded during the study. From the plasma concentration-time data, the following PK parameters will be determined, as data permit: $AUC_{(0-\infty)}$, area under the plasma concentration-time curve

from time of dose to last measurable concentration (AUC_(0-t)), area under the plasma concentration-time curve from time of dose to 24 hr (AUC₀₋₂₄), C_{max}, plasma DTG lag time for absorption (t_{lag}), time of occurrence of Cmax (t_{max}), terminal elimination phase half-life (t_{1/2}), terminal rate constant (λ_z), % of AUC_(0- ∞) that was extrapolated (%AUC_{ex}), apparent oral clearance (CL/F) and apparent volume of distribution during terminal phase (Vz/F), last quantifiable concentration (C_t), and concentration at 24 hours after dose administration (C₂₄).

Pharmacokinetic data will be listed and may be presented in graphical form and will be summarized descriptively. All PK data will be stored in the Archives, GlaxoSmithKline Research and Development (R&D).

The PK parameters (except for t_{max} and t_{lag}) for DTG will be log_e-transformed and separately analyzed using a mixed effects model with fixed effect terms for period and treatment for each treatment comparison. Subject will be treated as a random effect in the model. Point estimates and their associated 90% CIs will be constructed for the differences in PK parameter values between test and reference treatments. The point estimates and their associated 90% CIs will then be back-transformed to provide point estimates and 90% CIs for the ratios of PK parameters between test and reference treatments.

Further details will be provided in the Regulatory Analysis Plan (RAP).

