|                      | 
sampling times recorded during the study. From the plasma concentration-time data, the following PK parameters will be determined, as data permit: AUC(0-∞), area under the plasma concentration-time curve from time of dose to last measurable concentration (AUC(0-t)), area under the plasma concentration-time curve from time of dose to 24 hr (AUC0-24), maximum observed concentration (Cmax), plasma DTG lag time for absorption (tlag), time of occurrence of Cmax (tmax), terminal elimination phase half-life (t1/2), terminal rate constant (λz), %AUCex, apparent oral clearance (CL/F) and apparent volume of distribution during terminal phase (Vz/F), Ct, and concentration at 24 hours after dose administration (C24).
 
 
• Pharmacokinetic data will be listed and may be presented in graphical form and will be summarized descriptively. All PK data will be stored in the Archives, GlaxoSmithKline Research and Development (R&D) or their designee.
 
• The PK parameters except tmax and tlag) will be ln-transformed and separately analyzed using a mixed effects model with fixed effect terms for period and treatment for each treatment comparison. Subject will be treated as a random effect in the model. Point estimates and their associated 90% confidence intervals (CIs) will be constructed for the differences in PK parameter values between test and reference treatments. The point estimates and their associated 90% CIs will then be back-transformed to provide point estimates and 90% CIs for the ratios of PK parameters between test and reference treatments.
 
• Safety data will be presented in tabular format and summarized descriptively according to GSK's Integrated Data Standards Library (IDSL) standards. No formal statistical analysis of the safety data will be conducted.
 
• Palatability questionnaire variables will be summarized descriptively.
 
 |

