## 2. SUMMARY OF KEY PROTOCOL INFORMATION

### 2.1. Changes to the Protocol Defined Statistical Analysis Plan

The parameter “t” in the list of secondary endpoints in the protocol has been excluded as this does not represent an actual PK parameter and may be a typographical error in the protocol text. There were no other changes to or deviations from the originally planned statistical analysis specified in the protocol (Dated: 23/FEB/2017).

Listings of clinical laboratory data above a certain DAIDs toxicity grading are included in the outputs. Section 3.3.1 of the protocol indicated that these listings contain toxicities of grade 3 or higher; however, the listings will instead contain toxicities of grade 2 or higher.

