## 2.4. Statistical Hypotheses

This study is designed to estimate the relative BA of each test treatment to the reference treatment (A vs. B; C vs. E and D vs. E) in both study parts in the fasted state.

No formal hypothesis will be tested. For each pharmacokinetic endpoint (except for time of occurrence of Cmax [tmax] and tlag), point estimates and corresponding 90% CIs will be constructed for the ratio of the geometric mean of the test treatment to the geometric mean of the reference treatment,  $\mu(\text{test})/\mu(\text{reference})$ .

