**7.1.3.2. Statistical Analysis of Pharmacokinetic Parameters**

The following PK statistical analyses will only be performed, if sufficient data are available (i.e. if subjects have well defined plasma profiles).

| Pharmacokinetic Statistical Analyses                                                                                                                                                                                                          |  |
|-----------------------------------------------------------------------------------------------------------------------------------------------------------------------------------------------------------------------------------------------|--|
| Endpoint(s)                                                                                                                                                                                                                            |  |
| 
 
Plasma primary PK endpoints include AUC(0-∞), AUC(0-t) and Cmax of DTG, as data permit
 
                                                                                                      |  |
| Model Specification                                                                                                                                                                                                                    |  |
| 
 
In Part 1 of this study, the ln-transformed AUC(0-∞), AUC(0-t), and Cmax values for DTG will be analyzed separately using a mixed effects model, fitting fixed effect terms for period, and
 
 |  |

| Pharmacokinetic Statistical Analyses                                                                                                                                                                                                                                                                                                                                                                                                                                                                                                                                                                                                                                                                                                                                 |

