## 10.8. Appendix 8: Model Checking and Diagnostics for Statistical Analyses

### 10.8.1. Statistical Analysis Assumptions

|             |                                                                                            |
|-------------|--------------------------------------------------------------------------------------------|
| Endpoint(s) | 

• PK endpoints AUC(0-∞), AUC(0-t) and Cmax

 |
| Analysis    | 

• Mixed Effects

                            |

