| 3.4                          | PK         | PKPT3                         | Statistical Analysis of DTG Plasma Pharmacokinetic Parameters, Study Part 1                            | AUC(0-t), AUC(0-∞), and Cmax only by Treatment. Part 1 only. | SAC [1]                |
| 3.5                          | PK         | PKPT3                         | Statistical Analysis of DTG Plasma Pharmacokinetic Parameters, Study Part 2                            | AUC(0-t), AUC(0-∞), and Cmax only by Treatment. Part 2 only. | SAC [1]                |

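### Eight of the eleven PK parameters promised a model-based test/reference ratio with 90% CI have none in the SAP's analysis section or tables, and SAP 2.1 does not declare the reduction

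*SAP*

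**What the plan says.** **The broad promise.** Protocol 10.3.1.1 says the log-transformed PK parameters, tmax and tlag excepted, will be "separately analyzed using a mixed effects model with fixed effect terms for period and" treatment, with back-transformed ratios and 90% CIs. Protocol 10.1 makes the same commitment for each PK endpoint other than those two: "point estimates and corresponding 90% confidence intervals will be constructed for the ratio of the geometric mean of the test treatment" to that of the reference. The SAP repeats both statements. Its synopsis says: "The PK parameters except tmax and tlag) will be ln-transformed and separately analyzed using a mixed effects model". SAP 2.4 says: "For each pharmacokinetic endpoint (except for time of occurrence of Cmax [tmax] and tlag), point estimates and corresponding 90% CIs will be constructed".

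**The narrow specification.** SAP 7.1.3.2 gives as its endpoints: "Plasma primary PK endpoints include AUC(0-∞), AUC(0-t) and Cmax of DTG, as data permit". Its Part 1 model, Part 2 model and results presentation name the same three parameters. Appendix 8 (SAP 10.8.1) lists "PK endpoints AUC(0-∞), AUC(0-t) and Cmax" as the endpoints of the mixed-effects analysis. In SAP 10.10.5 the programming note for Table 3.4 is "AUC(0-t), AUC(0-∞), and Cmax only by Treatment. Part 1 only", and Table 3.5 carries the equivalent note for Part 2.

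**The declaration.** SAP 2.1 records two changes: the removal of t from the secondary endpoints, and a lower toxicity grade for the laboratory listings. On the statistical analysis it then says: "There were no other changes to or deviations from the originally planned statistical analysis specified in the protocol".

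**The concern.** The exception for tmax and tlag fixes the scope of the promise. Both are secondary endpoints, so excluding them makes sense only if the promise reaches the secondary list. The operative SAP text stops at the three primary parameters, and no other planned output fills the gap.

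Three things follow. First, the secondary PK objective in each part is a comparison of test with reference, and for eight parameters it is left with per-treatment descriptive summaries. Second, the SAP contradicts itself: read literally, SAP 2.4 calls for 11 modelled parameters, whereas Tables 3.4 and 3.5 call for 3. In an open-label study, leaving this unsettled allows the choice of secondary ratios to be made after results are seen. Third, the no-other-changes statement in SAP 2.1 is incorrect. A reader of the study report who relies on it would not know that planned analyses had been dropped.

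**Working it through.** **1. What is promised.** SAP Table 4 derives 13 parameters: AUC(0-t), AUC0-24, AUC(0-∞), %AUCex, Cmax, Ct, C24, tmax, tlag, t½, λz, CL/F and Vz/F. Removing tmax and tlag leaves 13 − 2 = 11. The contrasts are A vs B in Part 1, and C vs E and D vs E in Part 2, so 3 in all. Promised ratios with 90% CIs: 11 × 3 = 33.

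**2. What is planned.** Table 3.4 has 3 parameters × 1 contrast = 3. Table 3.5 has 3 parameters × 2 contrasts = 6. Total: 9.

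**3. Whether anything else supplies the rest.** The SAP's PK tables run from 3.1 to 3.5. Table 3.1 summarises concentrations, and Tables 3.2 and 3.3 summarise parameters by treatment. SAP section 8 covers safety and palatability only. Figure 3.7 plots individual C24 values by treatment without a ratio. Listing 37 gives individual parameter values. None of these reports a modelled ratio.

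**4. Shortfall.** 33 − 9 = 24, which is 8 parameters × 3 contrasts: AUC0-24, %AUCex, Ct, C24, t½, λz, CL/F and Vz/F.

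**5. How much of the shortfall matters.**

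| Step | Reason | Remaining |
|---|---|---|
| All missing ratios | 33 − 9 | 24 |
| Set aside %AUCex | SAP 10.3.3 lists it as not ln-transformed (itself at odds with the broad promise, and undeclared) | 24 − 3 = 21 |
| Set aside CL/F | ln(CL/F) = ln(dose) − ln(AUC(0-∞)); nominal doses are equal (5 × 10 = 50 mg; 5 × 5 = 25 mg), so ratio and CI limits are reciprocals of those in Tables 3.4 and 3.5 | 21 − 3 = 18 |
| Count λz and t½ once | t½ = ln 2 / λz, so each ratio is the reciprocal of the other | 18 − 3 = 15 |

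Of the 15, C24, AUC0-24 and t½ account for 3 × 3 = 9, and Vz/F and Ct for 2 × 3 = 6.

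**6. Why the descriptive table cannot supply the interval.** For a crossover ratio the 90% limits are exp(±t × s_w × √(2/N)) around the point estimate, where s_w is the within-subject SD on the log scale. The protocol's own precision figures follow this form. With CV 16.2%, s_w = √ln(1 + 0.162²) = 0.161.

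- Part 1, N = 12, 10 df: limits 0.888 and 1.127, against the stated 0.89 and 1.13.
- Part 2, N = 18, 32 df: limits 0.913 and 1.095, against the stated 0.91 and 1.10.

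The calculation needs s_w. Under SAP 10.3.3, Table 3.3 reports the geometric mean, its 95% CI, the SD of logged values and the between-subject CV, each by treatment. The variance of a within-subject difference is SD_T² + SD_R² − 2 cov(T, R), and the covariance is not reported. A crude ratio can be read from Table 3.3; the promised 90% CI cannot be obtained from it.

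**The case against.** The strongest defence is that the working instructions agree with one another. SAP 7.1.1 sends the reader to Appendix 10 for full details, Appendix 10 restricts the tables to three parameters, and the model text, results presentation and Appendix 8 match it. A programmer would probably produce three parameters; the synopsis and SAP 2.4 look like carried-over protocol wording. This makes the practical ambiguity smaller than a bare 11-versus-3 contrast suggests. It does not help the declaration: the more consistent the narrow reading is, the clearer it is that the SAP departs from the protocol while SAP 2.1 says it does not.

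A second argument is that 7.1.3.2 sits under primary analyses and need cover only primary endpoints. That fails, because protocol 10.3.1.1 sits under the same heading and covers everything but tmax and tlag, and no secondary PK model appears elsewhere in the SAP.

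A third concerns consequence, and much of it stands. No hypothesis is tested and no acceptance limit applies to a secondary parameter. With complete, balanced data the ratio of geometric means from Table 3.3 equals the model's point estimate, because each treatment occurs equally often in each period; only the interval is then lost. Listing 37 would let someone refit the model, though that would not be a planned analysis. Ct may be observed at different times in different profiles, so its ratio says little about bioavailability. Ranking C24, AUC0-24 and t½ above the rest is a statistical judgement; the documents single out only C24, through Figure 3.7.

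**Conclusion.** The concern holds. The protocol and two parts of the SAP commit to 33 ratios with 90% CIs; the SAP's analysis section and table list deliver 9, and the reduction is not declared. The nominal shortfall is 24. It falls to 15 once %AUCex and the reciprocal quantities are set aside, and 9 of those (C24, AUC0-24 and t½ over three contrasts) are of real interest. The step from 24 to 15 assumes equal nominal doses within each part, as the protocol specifies, and accepts the SAP's treatment of %AUCex as untransformed; the choice of the 9 is a judgement. The primary estimates, their precision and the sample size are unaffected. This should be corrected, but it does not threaten the main conclusions.

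**What to change.** Choose one scope and make every section agree with it before the analysis is run.

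- **Keep the protocol's scope.** Extend SAP 7.1.3.2, Appendix 8 and Tables 3.4 and 3.5 to run the same PROC MIXED model on AUC0-24, C24, t½, λz, CL/F, Vz/F and Ct, reporting A/B, C/E and D/E ratios with 90% CIs. State in SAP 2.1 that %AUCex is neither ln-transformed nor modelled.
- **Keep the three parameters.** Narrow the planned-analyses and hypothesis text in the SAP synopsis, and SAP 2.4, to AUC(0-∞), AUC(0-t) and Cmax. Declare in SAP 2.1 the departure from protocol 10.1 and 10.3.1.1, including the handling of %AUCex.

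The first option adds 7 × 3 = 21 estimates from an already specified model, on parameters that are already derived. The second is wording only, and leaves the secondary PK comparison openly descriptive. Neither needs new data.

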### 10.10.6. Pharmacokinetic Figures

| Pharmacokinetic : Figures                |            |                               |                                                                                               |                                          |                        |
|------------------------------------------|------------|-------------------------------|-----------------------------------------------------------------------------------------------|------------------------------------------|------------------------|
| No.                                      | Population | IDSL / TST ID / Example Shell | Title                                                                                         | Programming Notes                        | Deliverable [Priority] |
| Individual Concentration Plots    |            |                               |                                                                                               |                                          |                        |
| 3.1                                      | PK         | PKCF1X                        | Individual DTG Plasma Concentration-Time Plots by Subject (Linear and Semi-Logarithmic)       | Paginate by Subject                      | SAC [1]                |
| Mean / Median Concentration Plots |            |                               |                                                                                               |                                          |                        |
| 3.2                                      | PK         | PKCF2                         | Mean DTG Plasma Concentration-Time Plots by Treatment (Linear and Semi-Logarithmic)           | All treatments for each Part on one page | SAC [1]                |
| 3.3                                      | PK         | PKCF3                         | Median DTG Plasma Concentration-Time Plots by Treatment (Linear and Semi-Logarithmic)         | All treatments for each Part on one page | SAC [1]                |
| PK Analysis Plots                 |            |                               |                                                                                               |                                          |                        |
| 3.4                                      | PK         | PKPF3                         | Comparative Plot of Individual DTG Plasma Cmax by Treatment (Linear and Semi-Logarithmic)     | All treatments for each Part on one page | SAC [1]                |
| 3.5                                      | PK         | PKPF3                         | Comparative Plot of Individual DTG Plasma AUC(0-t) by Treatment (Linear and Semi-Logarithmic) | All treatments for each Part on one page | SAC [1]                |
| 3.6                                      | PK         | PKPF3                         | Comparative Plot of Individual DTG Plasma AUC(0-∞) by Treatment (Linear and Semi-Logarithmic) | All treatments for each Part on one page | SAC [1]                |
| 3.7                                      | PK         | PKPF3                         | Comparative Plot of Individual DTG Plasma C24 by Treatment (Linear and Semi-Logarithmic)      | All treatments for each Part on one page | SAC [1]                |

### 10.10.7. Exploratory Tables

| Exploratory : Tables |              |                               |                                                                          |                   |                        |
|----------------------|--------------|-------------------------------|--------------------------------------------------------------------------|-------------------|------------------------|
| No.                  | Population   | IDSL / TST ID / Example Shell | Title                                                                    | Programming Notes | Deliverable [Priority] |
| Palatability  |              |                               |                                                                          |                   |                        |
| 4.1                  | All Subjects | EXP_T1                        | Summary of Palatability Questionnaire Results (Part 2, Treatment C Only) |                   | SAC[1]                 |

### 10.10.8. ICH Listings

| ICH : Listings             |              |                               |                                                                  |                   |                        |
|----------------------------|--------------|-------------------------------|------------------------------------------------------------------|-------------------|------------------------|
| No.                        | Population   | IDSL / TST ID / Example Shell | Title                                                            | Programming Notes | Deliverable [Priority] |
| Randomisation       |              |                               |                                                                  |                   |                        |
| 1                          | All Subjects | CP_TA1                        | Listing of Randomised and Actual Treatment                       |                   | SAC [1]                |
| Subject Disposition |              |                               |                                                                  |                   |                        |
| 2                          | All Subjects | ES2                           | Listing of Reasons for Study Withdrawal                          |                   | SAC [1]                |
| 3                          | Screened     | ES7                           | Listing of Reasons for Screening Failure                         |                   | SAC [1]                |
| 4                          | Screened     | DV2                           | Listing of Important Protocol Deviations                         |                   | SAC [1]                |
| 5                          | All Subjects | IE4                           | Listing of Subjects with Inclusion/Exclusion Criteria Deviations |                   | SAC[1]                 |
| 6                          | Screened     | SP3                           | Listing of Subjects Excluded from Any Population                 |                   | SAC [1]                |
| Demographics        |              |                               |                                                                  |                   |                        |
| 7                          | All Subjects | DM4                           | Listing of Demographic Characteristics                           |                   | SAC [1]                |
| 8                          | All Subjects | DM10                          | Listing of Race                                                  |                   | SAC [1]                |

| ICH : Listings                 |              |                               |                                                                      |                   |                        |
|--------------------------------|--------------|-------------------------------|----------------------------------------------------------------------|-------------------|------------------------|
| No.                            | Population   | IDSL / TST ID / Example Shell | Title                                                                | Programming Notes | Deliverable [Priority] |
| Concomitant Medications |              |                               |                                                                      |                   |                        |
| 9                              | All Subjects | CM4                           | Listing of Concomitant Medications                                   |                   | SAC[1]                 |
| Exposure                |              |                               |                                                                      |                   |                        |
| 10                             | All Subjects | SAFE_L1                       | Listing of Exposure Data                                             |                   | SAC[1]                 |
| AEs                     |              |                               |                                                                      |                   |                        |
| 11                             | All Subjects | AE2                           | Listing of Relationship Between System Organ Class and Verbatim Text |                   | SAC[1]                 |
| 12                             | All Subjects | AE7                           | Listing of Subject Numbers for Individual Adverse Events             |                   | SAC[1]                 |
| 13                             | All Subjects | AE9CP                         | Listing of All Adverse Events                                        |                   | SAC[1]                 |
| 14                             | All Subjects | AE9CP                         | Listing of Study Drug Related Adverse Events                         |                   | SAC[1]                 |
| 15                             | All Subjects | SAFE_L2                       | Listing of Serious Adverse Events                                    |                   | SAC[1]                 |
| 16                             | All Subjects | AE9CP                         | Listing of Adverse Events Leading to Withdrawal from Study Drug      |                   | SAC[1]                 |
| 17                             | All Subjects | SAFE_L3                       | Listing of Liver Adverse Events                                      |                   | SAC[1]                 |

| ICH : Listings            |              |                               |                                                                                          |                   |                        |
|---------------------------|--------------|-------------------------------|------------------------------------------------------------------------------------------|-------------------|------------------------|
| No.                       | Population   | IDSL / TST ID / Example Shell | Title                                                                                    | Programming Notes | Deliverable [Priority] |
| Laboratory Values  |              |                               |                                                                                          |                   |                        |
| 18                        | All Subjects | LB6                           | Listing of Clinical Chemistry Toxicities of Grade 2 or Higher                            |                   | SAC [1]                |
| 19                        | All Subjects | LB6                           | Listing of All Clinical Chemistry Data for Subjects with Toxicities of Grade 2 or Higher |                   | SAC [1]                |
| 20                        | All Subjects | LB6                           | Listing of Haematology Toxicities of Grade 2 or Higher                                   |                   | SAC [1]                |
| 21                        | All Subjects | LB6                           | Listing of All Haematology Data for Subjects with Toxicities of Grade 2 or Higher        |                   | SAC [1]                |
| 22                        | All Subjects | LB6                           | Listing of Urinalysis Toxicities of Grade 2 or Higher                                    |                   | SAC [1]                |
| 23                        | All Subjects | LB6                           | Listing of All Urinalysis Data for Subjects with Toxicities of Grade 2 or Higher         |                   | SAC [1]                |
| Electrocardiograms |              |                               |                                                                                          |                   |                        |
| 24                        | All Subjects | EG6                           | Listing of Abnormal ECG Findings                                                         |                   | SAC [1]                |
| 25                        | All Subjects | EG6                           | Listing of All ECG Findings for Subjects with an Abnormal Finding                        |                   | SAC [1]                |
| 26                        | All Subjects | EG4                           | Listing of ECG Values of Potential Clinical Importance                                   |                   | SAC [1]                |
| 27                        | All Subjects | EG4                           | Listing of All ECG Values for Subjects with Any Value of Potential Clinical Importance   |                   | SAC[1]                 |

| ICH : Listings         |              |                               |                                                                                   |                                                                                                    |                        |
|------------------------|--------------|-------------------------------|-----------------------------------------------------------------------------------|----------------------------------------------------------------------------------------------------|------------------------|
| No.                    | Population   | IDSL / TST ID / Example Shell | Title                                                                             | Programming Notes                                                                                  | Deliverable [Priority] |
| Vital Signs     |              |                               |                                                                                   |                                                                                                    |                        |
| 28                     | All Subjects | VS5                           | Listing of Vital Signs of Potential Clinical Importance                           |                                                                                                    | SAC [1]                |
| 29                     | All Subjects | VS5                           | Listing of All Vital Signs for Subjects with Potential Clinical Importance Values |                                                                                                    | SAC [1]                |
| Liver Event     |              |                               |                                                                                   |                                                                                                    |                        |
| 30                     | All Subjects | LIVER5                        | Listing of Liver Monitoring/Stopping Event Reporting                              |                                                                                                    | SAC[1]                 |
| 31                     | All Subjects | MH3                           | Listing of Medical Conditions for Subjects with Liver Stopping Events             |                                                                                                    | SAC[1]                 |
| 32                     | All Subjects | SAFE_L5                       | Listing of Alcohol Intake at Onset of Liver Event                                 |                                                                                                    | SAC[1]                 |
| 33                     | All Subjects | PKCL1X                        | Listing of Plasma Concentration Data for Subjects with Liver Stopping Events      |                                                                                                    | SAC[1]                 |
| 34                     | All Subjects | LIVER7                        | Listing of Liver Biopsy Details                                                   |                                                                                                    | SAC[1]                 |
| 35                     | All Subjects | LIVER8                        | Listing of Liver Imaging Details                                                  |                                                                                                    | SAC[1]                 |
| Pharmacokinetic |              |                               |                                                                                   |                                                                                                    |                        |
| 36                     | PK           | PKCL1X                        | Listing of DTG Plasma Pharmacokinetic Concentration-Time Data by Treatment        | Please list all the concentration data including unscheduled. Repeat for all treatments and Parts. | SAC [1]                |
| 37                     | PK           | PKPL1X                        | Listing of Derived DTG Plasma Pharmacokinetic Parameters by Treatment             | Repeat for all treatments and Parts.                                                               | SAC [1]                |
| Exploratory     |              |                               |                                                                                   |                                                                                                    |                        |
| 38                     | All Subjects | EXP_L1                        | Listing of Palatability Questionnaire Results (Part 2, Treatment C Only)          |                                                                                                    | SAC[1]                 |
